10.8 Assessment of compliance

Subjects will be dosed on the research ward under the supervision of 2 suitably trained members of HMR staff.

11 Dietary and lifestyle restrictions

Subjects will abide by HMR house rules while on the ward.

Part A

Subjects will fast (no food or drink other than water) overnight for \geq 8 h before dosing until 2 h after dosing on Day 1. Standard meals will be provided at about 2, 4 and 10 h after dosing.

Part B

Morning dose: Subjects will fast (no food or drink other than water) overnight for ≥ 8 h before dosing until 2 h after dosing on Day 1 and Day 7. Standard meals will be provided at about 2, 4 and 10 h after dosing on Day 1 and Day 7.

Evening dose (if applicable): Subjects will fast (no food or drink other than water) for at least 2 h before and 2 h after dosing on Day 1 and 7.

At all other times during the study, standard meals will be given at usual times.

All study parts

During the study, subjects will fast for at least 8 h before laboratory safety blood samples are taken at screening, on admission (Day -1), and Follow-up.

No alcoholic drinks or smoking will be allowed during the period from 24 h before admission until follow-up. No caffeinated drinks will be allowed from 24 h before admission until discharge from the ward (Day 2 in Part A and Day 8 in Part B). No strenuous exercise will be allowed from 2 days before screening until follow-up.

Subjects will rest in bed in the supine position during and until ≥ 5 min after dosing.

Subjects must not sunbathe or use a sunbed during the study.

Subjects must use a reliable method of contraception¹⁰, as follows.

Men

Male subjects must not plan to father a child, or donate sperm, from dosing until 3 months after their (last) dose.

Male subjects must not have sex without using a condom, from dosing until 3 months after their (last) dose, if their partner is a woman of childbearing potential. They do not need to use any contraception if: they've had a vasectomy, and surgical success has been confirmed by medical assessment; their partner has had a bilateral tubal ligation; or their partner is not of childbearing potential. Partners who are not of childbearing potential are defined as: men; post-menopausal women (no menstrual periods for at least 12 months); or women who have no uterus, ovaries or fallopian tubes.

Women

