6. Laboratory safety tests consist of biochemistry, haematology and urinalysis in serum. They will be done at screening; on Day -1, and before and at 8 and 24 h after dosing on Day 1; and at follow-up. Subjects should fast for ≥ 8 h before laboratory safety tests at screening, admission (Day -1), and follow-up.
7. Pregnancy tests in women of child-bearing potential only.
8. FSH tests in post-menopausal women at screening only.
9. FEV₁ and FVC will be measured at screening; at 4, 8, 12 and 24 after dosing on Day 1; and at follow-up.
10. If a subject develops symptoms of COVID-19, ad hoc SARS-CoV-2 infection tests will be done.
11. Blood samples for assay of Neumifil will be taken before and at 1, 2, and 3 h after dosing on Day 1.

When more than one procedure is scheduled at a specific time point, procedures should be done in the following order: ECG, vital signs, blood samples (at the scheduled time), then spirometry. Blood sampling should be done on time. Other procedures should be done as close as possible to the scheduled time point.

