6. ECGs will be recorded at screening; before and at 2.5 h after dosing on Days 1 and 7; and at follow-up. Triplicate recordings (to at least 2 min apart) will be made at screening; single recordings will be done at all other time points. Recordings should be made with subjects in a supine position, after resting for 5 min.
7. Laboratory safety tests consist of biochemistry, haematology and urinalysis in serum. They will be done at screening; on Day –1; at 24 h after dosing on Day 1; on Day 8; at the outpatient visit; and at follow-up. Subjects should fast for \geq 8 h before laboratory safety tests at screening, admission (Day –1), and follow-up.
8. Pregnancy tests in women of child-bearing potential only.
9. FSH tests in post-menopausal women at screening only.
10. FEV₁ and FVC will be measured at screening; at 4, 8, 12 and 24 after dosing on Days 1 and 7; at the outpatient visit; and at follow-up.
11. If a subject develops symptoms of COVID-19, ad hoc SARS-CoV-2 infection tests will be done.
12. Self-assessment nasal tolerability questionnaires will be completed at 1 and 12 h post dose after each dose of Neumifil.
13. Once-daily intranasal doses of Neumifil.
14. Blood samples for assay of Neumifil will be taken:
 - before and at 1, 2, and 3 h after dosing on Days 1 and 7
15. Blood samples for assay of Neumifil ADAs will be taken before dosing on Day 1, and at follow-up.
16. Nasal wick samples will be taken before the evening meal on Day –1, or not less than 2 h after food at all timepoints.

When more than one procedure is scheduled at a specific time point, procedures should be done in the following order: ECG, vital signs, blood samples (at the scheduled time), then spirometry. Blood sampling should be done on time. Other procedures should be done as close as possible to the scheduled time point.

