16.1.6.2 Clinical laboratory evaluations

Data from haematology and clinical chemistry will be summarised by treatment.

Any laboratory value outside the reference interval for that variable will be flagged with an 'H' if it is higher than the reference interval, and with an 'L' if it is lower. Additionally, if, during the course of the trial, a variable changes from baseline by more than a predetermined amount (as defined by the principal investigator), that value will receive a flag 'I' if increased, or 'D' if decreased. Therefore, if a value both falls outside the reference interval and alters from the baseline value by more than the predetermined amount, it will attract a double flag and will be considered to be of potential clinical importance (PCI).

All laboratory values of PCI will be listed. In a separate listing, laboratory values of PCI will be listed with all related laboratory results (ie haematology or clinical chemistry). Frequencies of laboratory values of PCI will be summarised.

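### Laboratory baselines are fasted but several post-dose samples need not be, so glucose and triglyceride change flags, above all at 8 h in Part A, may reflect meals

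*Combined protocol and SAP*

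**What the plan says.** **Fasting.** The laboratory fasting rule in section 11 is that "subjects will fast for at least 8 h before laboratory safety blood samples are taken at screening", and likewise on Day -1 and at follow-up. Note 6 (Part A) and note 7 (Part B) of the schedules of procedures name the same three occasions. So does the footnote to Table 7, which is attached to glucose but not to triglycerides, although both are in the panel.

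**Meals.** The Part A dosing fast runs overnight until 2 h after the dose, and "Standard meals will be provided at about 2, 4 and 10 h after dosing". Part B has the same meal times on Days 1 and 7 for a morning dose. Otherwise, "At all other times during the study, standard meals will be given at usual times".

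**Samples.** After screening and Day -1, Part A takes laboratory samples "before and at 8 and 24 h after dosing on Day 1; and at follow-up". Part B takes them "at 24 h after dosing on Day 1; on Day 8; at the outpatient visit; and at follow-up", with no pre-dose sample on Day 1.

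**Analysis.** Section 16.1.4 takes the last value before dosing as baseline. Section 16.1.6.2 flags values outside the reference interval (H or L). It applies a second flag (I or D) if "a variable changes from baseline by more than a predetermined amount", the amount being left to the principal investigator. A value with both flags is of PCI; such values are listed and their frequencies summarised. Fasting status is not mentioned.

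**The concern.** Glucose and triglycerides depend on recent food. Comparing a sample taken after meals with an overnight-fasted baseline mixes any drug effect with a food effect. The plan neither controls the food effect at these time points, nor says that fasting status will be recorded, nor separates it in the tables.

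The timing adds to the problem. The uncontrolled samples are those taken during or soon after dosing, while the follow-up sample is fasted. A food-driven rise would appear after dosing and disappear at follow-up, which is also how a reversible drug effect would look.

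Laboratory safety tests are among the data that the Safety Review Group (SRG) must review before each dose decision (section 8.5.1). Each group has only 2 placebo subjects (A1–A3, B1–B3) or 3 (A4, A5), so one review gives little information on what happens without the drug.

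**Working it through.** The plan states no flag rate, threshold or sample-size calculation, so there is no figure of its own to reproduce. The check has two parts: the schedule, which rests on the documents, and an illustration of size, which rests on assumptions.

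**1. Schedule against the fasting rules**

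| Sample | Part A | Part B |
|---|---|---|
| Screening | fast required | fast required |
| Day -1 | fast required | fast required (baseline) |
| Pre-dose Day 1 | fasted through the dosing fast (baseline) | no sample |
| 8 h | fed by protocol | no sample |
| 24 h (Day 2) | no rule | no rule |
| Day 8 | no sample | no rule |
| Outpatient visit | no sample | no rule |
| Follow-up | fast required | fast required |

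Each part has 6 samples, which agrees with the 6 biochemistry tests in Tables 8 and 9.

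- Post-dose samples with no fasting rule: 2 of 3 in Part A and 3 of 4 in Part B.
- Planned number: 36 × 2 = 72 in Part A; 24 × 3 = 72 in Part B.
- Part A 8 h sample: 8 − 4 = about 4 h after the second meal, so all 36 planned samples are fed.
- Part A 24 h sample: 24 − 10 = about 14 h after the last listed meal. It is fasted in practice unless something is eaten first, which the protocol allows. The same holds in Part B after a morning dose on Day 1, and on Day 8 if that sample is drawn 24 h after the Day 7 dose.

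**2. Illustration for one fed triglyceride sample**

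None of these inputs is in the documents: fasting median 1.0 mmol/L, upper reference limit 1.7 mmol/L, change flag at +50%, log-scale SD 0.40 between and 0.20 within subjects, and subjects in range at screening. With meal effect m:

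- baseline = exp(b + e₁); fed sample = (1 + m) × exp(b + e₂)
- b ~ N(0, 0.40²); e₁ and e₂ ~ N(0, 0.20²), independent
- false double flag: fed sample > 1.7 and > 1.5 × baseline

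Simulation gives p, the chance per subject. The rest follows from p:

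- at least one among k active subjects: 1 − (1 − p)^k
- at least one on active and none among j placebo subjects: [1 − (1 − p)^k] × (1 − p)^j

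| Meal effect | p | ≥1 of 4 active (A1–A3) | ≥1 of 6 active (A4, A5) | Active only, 4 + 2 | Active only, 6 + 3 |
|---|---|---|---|---|---|
| none | 1.4% | 5% | 8% | 5% | 8% |
| +20% | 6.0% | 22% | 31% | 19% | 26% |
| +40% | 15.1% | 48% | 63% | 35% | 38% |
| +60% | 27.6% | 73% | 86% | 38% | 32% |

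For example, at +40% with 6 active and 3 placebo subjects: 1 − 0.849⁶ = 0.63, and 0.63 × 0.849³ = 0.38.

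Over A1–A5 there are 3 × 4 + 2 × 6 = 24 active and 3 × 2 + 2 × 3 = 12 placebo subjects. At +40% the expected false flags are 24 × 0.151 = 3.6 and 12 × 0.151 = 1.8. The ratio is the 2:1 allocation ratio, so neither arm is favoured.

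**The case against.** The case on the other side has real force, and four readings that a reader might draw go too far.

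- **That all the post-dose samples are fed.** The documents show this only for Part A at 8 h. The 24 h samples, and a Day 8 sample drawn at 24 h, may well be fasted; the outpatient visit is unregulated rather than shown to be fed. Treating three samples as fed would raise the illustrated rates to 14%, 30% and 47%, but the documents do not show that this happens to any subject.
- **That the active-placebo comparison is biased.** It is not. Randomised placebo subjects have the same meals and sampling times.
- **That false PCI counts are established.** PCI needs both flags. The change threshold and reference interval are not given, and a threshold could be set wide enough to allow for meals.
- **That the primary endpoint is compromised.** Section 7.2.1 concerns clinically significant change, which is a matter of judgement, and section 14.2 sets further conditions before an abnormal result becomes an adverse event. PCI flags feed listings and frequency tables; nothing makes their count an escalation rule.

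It is also fair that a reviewer who knows the meal schedule could recognise a rise confined to 8 h, that only two analytes are clearly involved, and that section 16.1.2 plans no hypothesis test.

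What the objection leaves standing is narrower. The 8 h values are compared with a fasted baseline, fasting elsewhere is uncontrolled, and the flag rule makes no allowance for either. Pooled placebo data help at the end of the study, but less at a single SRG review.

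**Conclusion.** The concern holds as a minor one. The mismatch between a fasted baseline and post-dose samples with no fasting rule is certain from the text in both parts; an actual fed sample is certain only at 8 h in Part A. Glucose and triglyceride flags there may reflect meals, and elsewhere their meaning depends on unregulated breakfast times.

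The consequence is extra noise and possibly inflated PCI counts, which could mislead a review of one small group. The percentages show only what is plausible for triglycerides under the stated assumptions. No rate can be derived from the documents, and none was calculated for glucose. Even with no meal effect the same model gives an 8% chance of at least one false flag among 6 active subjects, so only the excess over that belongs to food.

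**What to change.** 1. In section 11, in notes 6 and 7 of the schedules and in the Table 7 footnote, extend the 8 h fast to the laboratory samples at 24 h (Day 2) in both parts and at Day 8 and the outpatient visit in Part B. On the ward this means drawing the sample before breakfast.
2. Attach the Table 7 fasting footnote to triglycerides as well as glucose.
3. For the Part A 8 h sample, keep listing all values and out-of-range flags, but report glucose and triglyceride change and PCI flags separately as non-fasted rather than pooling them with fasted comparisons. This can be written into the SAP, which section 16.1.1 places before first database lock.
4. If the extra fasts are not adopted, the minimum is to record time since last meal at each laboratory sample and present these two analytes by fasting status.

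The cost is one additional fast before the Part B outpatient visit, slightly later breakfasts on the ward and a small change to the flag tables. No extra blood sample, visit or subject is needed.

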12.1 Schedule of procedures

12.1.1 Part A

Period:	Screening 1	Study session											Follow-up			
		Day:	-35 to -2	-1	Pre	0	0.25	0.5	1	2	2.5	3	4	8	12	24
Time (h)																
Informed consent	X															
Inclusion/exclusion criteria	X	X	X													
Medical history	X															
Admission		X														
Inpatient stay			◀											▶		
Discharge																X
Safety assessments																
Physical examination ²	X	X							X							X
Height & weight ³	X	X														X
Vital signs ⁴	X	X	X						X			X	X	X	X	X
12-lead ECG ⁵	X		X							X						X
Serology	X															
Laboratory safety tests ⁶	X	X	X										X		X	X
Pregnancy ⁷	X	X														X
FSH ⁸	X															
Urine drug, alcohol and cotinine tests	X	X														
Spirometry ⁹	X											X	X	X	X	X
Nasal examination	X	X														X
SARS-CoV-2 infection test ¹⁰	X	X														X
Self-assessment nasal tolerability rating scale								X								X
Dosing																
Intranasal Neumifil					X											
Neumifil PK																
PK sampling ¹¹				X					X	X		X				

Abbreviations: ECG: electrocardiogram; FSH: follicle-stimulating hormone; PK: pharmacokinetics; AEs: adverse events.

Notes:

1. Screening will be within 35 days before dosing
2. Full physical examinations will be done at screening and on Day -1. Brief (symptom-directed) physical examinations will be done at all other timepoints.
3. Height measured at screening only.
4. Vital signs consist of: systolic and diastolic blood pressure, heart rate, pulse oximetry, temperature and respiratory rate. They will be assessed at screening; on Day -1, and before and at 2, 4, 8, 12 and 24 h after dosing on Day 1; and at follow-up. Triplicate measurements (at least 2 min apart) will be made at screening and before dosing. Single measurements will be made at all other time points. Measurements should be made with subjects in a supine position, after resting for 5 min.
5. ECGs will be recorded at screening; before and at 2.5 h after dosing on Day 1; and at follow-up. Triplicate recordings (at least 2 min apart) will be made at screening and before dosing; single recordings will be done at all other time points. Recordings should be made with subjects in a supine position, after resting for 5 min.
6. Laboratory safety tests consist of biochemistry, haematology and urinalysis in serum. They will be done at screening; on Day -1, and before and at 8 and 24 h after dosing on Day 1; and at follow-up. Subjects should fast for ≥ 8 h before laboratory safety tests at screening, admission (Day -1), and follow-up.
7. Pregnancy tests in women of child-bearing potential only.
8. FSH tests in post-menopausal women at screening only.
9. FEV₁ and FVC will be measured at screening; at 4, 8, 12 and 24 after dosing on Day 1; and at follow-up.
10. If a subject develops symptoms of COVID-19, ad hoc SARS-CoV-2 infection tests will be done.
11. Blood samples for assay of Neumifil will be taken before and at 1, 2, and 3 h after dosing on Day 1.

When more than one procedure is scheduled at a specific time point, procedures should be done in the following order: ECG, vital signs, blood samples (at the scheduled time), then spirometry. Blood sampling should be done on time. Other procedures should be done as close as possible to the scheduled time point.

12.1.2 Part B

Period: Day:	Screening ¹	Study session									OP 14 to 16	Follow-up ² 21 to 23
		-35 to -2	-1	1	2	3	4	5 to 6	7	8		
Informed consent	X											
Inclusion/exclusion criteria	X	X	X									
Medical history	X											
Admission		X										
Inpatient stay			←						→			
Discharge										X		
Safety assessments												
Physical examination ³	X	X	X							X		X
Height & weight ³	X	X									X	X
Vital signs ⁵	X	X	X	X					X	X	X	X
12-lead ECG ⁶	X		X						X			X
Serology	X											
Laboratory safety tests ⁷	X	X		X					X		X	X
Pregnancy ⁸	X	X										X
FSH test ⁹	X											
Urine drug, alcohol and smoking tests	X	X										
Spirometry ¹⁰	X		X	X					X	X	X	X
Nasal examination	X	X		X					X		X	X
SARS-CoV-2 infection test ¹¹	X	X							X		X	X
Self-assessment nasal tolerability rating scale ¹²			X	X	X	X	X	X	X			
Dosing												
Intranasal Neumifil ¹³			X	X	X	X	X	X	X			
Neumifil PK												
PK sampling ¹⁴			X						X			
Immunogenicity												
ADA sampling ¹⁵			X									X
Pharmacodynamics												
Nasal wick sampling ¹⁶		X							X			X
Ongoing subject review												
Concomitant medicines	←								→			
AEs	←								→			

Abbreviations: OP: outpatient visit; ECG: electrocardiogram; FSH: follicle-stimulating hormone; PK: pharmacokinetics; ADA: anti-drug antibodies; AEs: adverse events.

Notes:

1. Screening will be within 35 days before dosing
2. Follow up will be 14 days (\pm 1 day) after the last dose.
3. Full physical examinations will be done at screening and Day –1. Brief (symptom-directed) physical examinations will be done at all other timepoints. Subjects may be referred for chest x-ray if the chest examination results are of clinical concern.
4. Height measured at screening only.
5. Vital signs consist of: systolic and diastolic blood pressure, heart rate, temperature, pulse oximetry and respiratory rate. They will be assessed at screening; on Day –1, and before and at 2, 4, 8, 12 and 24 h after dosing on Days 1 and 7; at the outpatient visit; and at follow-up. Triplicate measurements (at least 2 min apart) will be made at screening and before dosing. Single measurements will be made at all other time points. Measurements should be made with subjects in a supine position, after resting for 5 min.
6. ECGs will be recorded at screening; before and at 2.5 h after dosing on Days 1 and 7; and at follow-up. Triplicate recordings (to at least 2 min apart) will be made at screening; single recordings will be done at all other time points. Recordings should be made with subjects in a supine position, after resting for 5 min.
7. Laboratory safety tests consist of biochemistry, haematology and urinalysis in serum. They will be done at screening; on Day –1; at 24 h after dosing on Day 1; on Day 8; at the outpatient visit; and at follow-up. Subjects should fast for \geq 8 h before laboratory safety tests at screening, admission (Day –1), and follow-up.
8. Pregnancy tests in women of child-bearing potential only.
9. FSH tests in post-menopausal women at screening only.
10. FEV₁ and FVC will be measured at screening; at 4, 8, 12 and 24 after dosing on Days 1 and 7; at the outpatient visit; and at follow-up.
11. If a subject develops symptoms of COVID-19, ad hoc SARS-CoV-2 infection tests will be done.
12. Self-assessment nasal tolerability questionnaires will be completed at 1 and 12 h post dose after each dose of Neumifil.
13. Once-daily intranasal doses of Neumifil.
14. Blood samples for assay of Neumifil will be taken:
 - before and at 1, 2, and 3 h after dosing on Days 1 and 7
15. Blood samples for assay of Neumifil ADAs will be taken before dosing on Day 1, and at follow-up.
16. Nasal wick samples will be taken before the evening meal on Day –1, or not less than 2 h after food at all timepoints.

When more than one procedure is scheduled at a specific time point, procedures should be done in the following order: ECG, vital signs, blood samples (at the scheduled time), then spirometry. Blood sampling should be done on time. Other procedures should be done as close as possible to the scheduled time point.

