7.2 Endpoints

7.2.1 Primary endpoints

Safety and tolerability:

Clinically significant changes in: vital signs (heart rate, blood pressure, respiratory rate, pulse oximetry and temperature), 12-lead ECG, FEV₁, FVC, physical examination, nasal examination, laboratory safety tests (haematology, biochemistry and urinalysis), tolerability questionnaire, AEs and serious AEs (SAEs). Safety endpoints will be assessed up to 7 days after dosing in Part A or up to 14 days after the last dose in Part B.

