Enrolment of up to 24 healthy subjects is planned, in up to 3 groups of 8 subjects (Groups B1–B3).

Subjects will receive once-daily intranasal doses of Neumifil or placebo for 7 days. In each group, 6 subjects will receive Neumifil and 2 will receive matching placebo.

[figure not shown]
Part B can start before completion of Part A. The starting dose level (dose and dose regimen) for Group B1 will be decided after review of safety and tolerability data from at least 3 dose levels in Part A, and will be no higher than a dose that has previously been shown to cause no safety concerns in Part A (see section 8.5.3). An additional dose level may be explored in 1 optional group of up to 8 subjects (Group B4). Subsequent doses levels, including maximum duration of dosing, will be determined as described in Part A.

Subjects will be screened within 35 days before their dose of trial medication.

[figure not shown]
Subjects will be resident on ward from 1 day before their dose (Day –1) until about 24 h after their last dose (Day 8). Subjects will attend an outpatient visit at 7–8 days after their last dose (Days 15–16). They will then return for a follow-up visit at 13–15 days after their dose (Days 21–23).

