8.5 Criteria for dose selection

8.5.1 *Review of data by the SRG*

During the study, the dose level (dose and [if applicable] dose regimen) will be increased only if the safety and tolerability of the previous dose level is acceptable.

All dose levels will be selected by the SRG, which will include (as a minimum) the principal investigator (or delegate) and the sponsor's medically qualified

representative (or delegate). Each dose decision will be made and documented in line with HMR SOPs.

Before confirming the dose level for any group, the SRG will review, as a minimum, safety and tolerability data from the previous dose level and (if different) the highest dose level tested to date, as described below. Safety and tolerability data obtained from the previous group(s) will also be reviewed, if applicable. All data used to support dose selection will be quality checked.

Review of safety and tolerability data

The SRG will review (as a minimum) safety and tolerability data, up to 7 days after (final) dosing, from at least 4 evaluable subjects who have received active treatment at the highest dose level tested to date. An evaluable subject is one who completes dosing, has undergone procedures until 7 days after (final) dosing, and has no major protocol deviations. To maintain blinding, data from at least 6 subjects in each group of 6 (Groups A1–A3) or 8 (Groups B1–B3), or from at least 7 subjects in each group of 9 (Groups A4 and A5), must be reviewed to ensure that the dataset includes at least 4 evaluable subjects on active treatment. If fewer subjects than planned are dosed, any subjects required to complete the group may be dosed in parallel with subsequent groups.

The safety data reviewed will include, as a minimum:

- AEs and SAEs, including description, intensity, onset, duration, and relationship to treatment
- vital signs
- 12-lead safety ECG
- laboratory safety tests
- physical examination
- nasal examination
- FEV₁
- tolerability questionnaire

Review of pharmacokinetic data

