Laboratory assessments (haematology, biochemistry and urinalysis), physical examinations, 12-lead ECGs, vital signs (heart rate, blood pressure, respiratory rate, pulse oximetry and temperature), nasal examinations and spirometry will be done before and during dosing and frequently until the subject's last visit in each study part. Subjects will complete a tolerability questionnaire post-dose after each dose of Neumifil. AEs will be recorded from screening until the subject's last visit in each study part.

The schedules of procedures are in sections 12.1.1 (Part A) and 12.1.2 (Part B).

Laboratory safety variables to be assessed during the study are in Table 7.

Throughout the study, AEs and concomitant medication will be documented as they are reported by the subjects. Subjects will be questioned about AEs when procedures are done, and when they return to the ward for outpatient visits (Part B only), and at follow-up.

Plasma concentration of Neumifil

Blood samples for assay of Neumifil will be taken before and up to 3 h after dosing on Day 1 (Part A) and Days 1 and 7 (Part B).

[figure not shown]
Immunogenicity

Blood samples for assay of Neumifil ADAs will be taken before dosing on Day 1 and on Day 22 (Part B only).

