17. The Human Medicines (Amendment etc) (EU Exit) Regulations 2019: Statutory instrument 2019 No 775.
18. The Human Medicines (Amendment etc) (EU Exit) Regulations 2020: Statutory instrument 2019 No 1488.
19. Standard operating procedures for Research Ethics Committees in the UK, Research Ethics Service.
20. Structure and content of clinical study reports. ICH harmonised tripartite guideline E3, 1995.
21. Guidelines for Phase 1 Clinical Trials, 2018 Edition. Association of the British Pharmaceutical Industry.

22 Appendix 1: Subject self-reported dosing and post-dosing experience

Study PNG-NMF-101

Subject Number:

Please assess the following aspects of your dosing and post dosing experience, following administration of Neumifil or placebo. A numerical score of 0 to 10 is used for each parameter, as described below

The statements are as follows.

Since your last dose have you experienced any of the following? –

1. Pain or stinging in the nose?

Score

0 No Pain or stinging in the nose has been experienced

10 Pain or stinging most extreme imaginable and you would not want to experience it again

2. Burning sensation or sensation of heat/hotness in the nose?

Score

0 No Burning sensation or sensation of heat/hotness in the nose has been experienced

10 Burning sensation or sensation of heat/hotness in the nose most extreme imaginable and you would not want to experience it again

3. Bleeding from the nose.

Score

0 Bleeding has not experienced

10 Bleeding that requires medical intervention and packing of the nose.

4. Sensation of needing to blow your nose?

Score

0 The sensation of needing to blow your nose has not been experienced

10 The sensation to blow your nose is persistent and affects your normal life to the extent you would not want to experience it again

5. General irritation in nose.

Score

0 No irritation has been experienced

10 Irritation of the nose is the most extreme imaginable and you would not want to experience it again

6. Sneezing**Score**

0 Sneezing is not experienced

10 Sneezing most extreme imaginable and you would not want to experience it again

7. Marked change in your sense of smell or taste**Score**

0 No change in your sense of smell or taste

10 Complete loss of smell or taste

8. Unpleasant taste.**Score**

0 No unpleasant taste

10 Unpleasant taste is so bad you would not want to experience it again

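### In Part B the nasal tolerability questionnaire, a primary safety endpoint, stops 12 h after the last dose and, with once-daily dosing, does not ask about 12–24 h after a dose

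*Combined protocol and SAP*

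**What the plan says.** Section 7.2.1 includes the questionnaire in the primary safety endpoints ("tolerability questionnaire, AEs and serious AEs (SAEs") and gives one window for all of them: "assessed up to 7 days after dosing in Part A or up to 14 days after the last dose in Part B". Section 8.5.1 lists the questionnaire in the minimum data for the Safety Review Group (SRG), which reviews "safety and tolerability data, up to 7 days after (final) dosing".

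The schedule is narrower. Note 12 in section 12.1.2 reads: "Self-assessment nasal tolerability questionnaires will be completed at 1 and 12 h post dose after each dose of Neumifil". The questionnaire row of the Part B table is marked like the dosing row, with nothing on Day 8, at the outpatient visit or at follow-up. Section 12 agrees: "Subjects will complete a tolerability questionnaire post-dose after each dose of Neumifil".

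The form in Appendix 1 opens with: "Since your last dose have you experienced any of the following". The planned regimen in 8.1.2 is: "Subjects will receive once-daily intranasal doses of Neumifil or placebo for 7 days". Sections 8.5.3 and 10.6 also allow twice-daily dosing.

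Three other provisions bear on the point:

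- Section 14.2 makes any questionnaire score above 0 an AE.
- The nasal examination in 12.4 asks about tenderness, soreness or irritation and about change in smell.
- Section 12 has subjects questioned about AEs at procedures, at outpatient visits and at follow-up.

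**The concern.** The stated windows for the endpoint and for the SRG review extend well past the last time the instrument is given. Local nasal effect is a natural focus for an intranasal product. Section 6.2.5 reports inflammatory and reactive changes in the nasal mucosa in all treated groups of the 28-day rat study. Persistence, delayed onset and recovery after repeated dosing are therefore things Part B should be able to describe.

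As scheduled, the 0–10 scale can describe none of these beyond 12 h after a dose. Because every positive score becomes an AE, nasal AE counts during dosing come from prompted, item-by-item forms as well as open questions. Counts after dosing come from examination questions and open questions only. A fall in nasal AEs once dosing stops would then mix true recovery with withdrawal of the instrument. Section 16.1.6 names no summary of the scores themselves, so the AE tables are their only specified route into the analysis, although 16.1.1 leaves a separate statistical analysis plan to be written.

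**Working it through.** The plan gives no figure for questionnaire coverage, no sample size calculation and no hypothesis, so there is nothing to reproduce. The check is a count of hours, followed by a comparison of items.

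**Inputs.** 7 doses, 24 h apart (8.1.2); forms at 1 h and 12 h after each dose (note 12); recall since the last dose (Appendix 1); 14-day endpoint window (7.2.1); 7-day SRG window (8.5.1).

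**Reach of each form.** Read literally, the 1 h form covers 0–1 h and the 12 h form covers 0–12 h. The next form comes 1 h after the next dose, and its recall restarts at that dose. So 12–24 h after each dose is not asked about.

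**Coverage, once daily, literal recall**

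- Hours covered: 7 × 12 = 84 h.
- Dosing period, first dose to 24 h after the last: 7 × 24 = 168 h; 84/168 = 50%.
- After the last dose, endpoint window: 14 × 24 = 336 h; 12/336 = 3.6%.
- After the last dose, SRG window: 7 × 24 = 168 h; 12/168 = 7.1%.
- First dose to 14 days after the last: 6 × 24 + 14 × 24 = 480 h; 84/480 = 17.5%. With follow-up at 15 or 13 days this is 84/504 = 16.7% or 84/456 = 18.4%.

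**Sensitivity to the reading**

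- If subjects take the last dose at the 1 h form to mean the previous day's dose, the between-dose gap closes: 6 × 24 + 12 = 156 h; 156/480 = 32.5%. The gap after treatment is unchanged.
- With twice-daily dosing (14 doses, assumed 12 h apart) the between-dose gap also closes: 13 × 12 + 12 = 168 h of 13 × 12 + 336 = 492 h, or 34.1%. The gap after treatment is again unchanged.

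**Items left without a direct question.** The form has eight items. The nasal-examination questions overlap with pain or stinging, general irritation, and the smell half of the smell-or-taste item. Five items have no counterpart: burning, bleeding, need to blow the nose, sneezing and unpleasant taste. In the Part B table the nasal-examination row is marked like the laboratory row, which note 7 places at 24 h after the Day 1 dose, on Day 8, at the outpatient visit and at follow-up. On that reading, no nasal-examination question falls between Day 2 and Day 8.

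**Missing, not zero.** Let p be the true share of subjects with a new late symptom and s the share of those caught by the remaining questions. The recorded rate is p × s, which is zero only if s = 0. As an illustration, assume p = 0.2 and s = 0.25 to 0.5. The recorded rate is then 5–10%. The chance of at least one recorded case is:

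- 6 active subjects (one group): 1 − 0.95^6 = 27% to 1 − 0.90^6 = 47%, against 1 − 0.80^6 = 74% with full capture.
- 18 active subjects (B1–B3): 1 − 0.95^18 = 60% to 1 − 0.90^18 = 85%, against 1 − 0.80^18 = 98%.

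The documents give neither p nor s.

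**The case against.** The best defence is that the 14-day sentence in 7.2.1 is collective. Section 12 separates the schedules: laboratory tests, examinations and spirometry run to the last visit, while the questionnaire follows each dose. On that view this is loose drafting. That is plausible, but 8.5.1 has the same mismatch, and the text still needs reconciling.

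Other collection also continues. An AE that began as a score has its onset, end and outcome recorded (14.2). AE questioning runs to the last visit, and 12.3 lets follow-up be extended for an unresolved AE. Nasal examinations add speculum inspection. This stands: a symptom already recorded stays under observation, so the main loss is in new onsets beyond 12 h and in scored recovery.

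Forms are given at the same times in both blinded arms, so their timing alone does not bias active against placebo. Section 16.1.6.1 plans no comparison of AEs during and after dosing. Section 12.2 permits extra time points, but schedules none.

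A reader might infer three stronger things that the documents do not support:

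- That solicited symptom rates fall to zero by construction. Later scores are missing, nothing says unasked periods count as symptom-free, and some solicited questions remain.
- That symptoms 12–24 h after any dose are never solicited. Nasal examinations appear to fall about 24 h after the first and last doses, and twice-daily dosing closes the between-dose gap. The Part A table is too broken to place its later form.
- That the SRG would take absent scores as good tolerability. No text says so, and 8.5.1 also gives it AEs with onset and duration, and nasal examinations.

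**Conclusion.** The point holds for Part B as a gap in ascertainment of a listed primary endpoint. After the last dose the questionnaire covers 3.6% of the stated 14-day window and 7.1% of the SRG's 7-day window, under either dosing frequency and either reading of the recall wording. The further 12–24 h gap, which leaves 50% of the dosing period covered, depends on once-daily dosing and on subjects taking the recall wording literally.

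These are shares of clock time, not of symptoms missed. If most symptoms arise within 12 h of a dose, the loss is small; the documents do not say when they arise. What is certain is that five of the eight items have no direct question beyond that point, that recovery cannot be shown on the 0–10 scale, and that nasal AE counts during and after dosing come from different methods. The trial is exploratory and no hypothesis test is affected. This should be corrected because it is cheap and concerns local tolerability, but it does not threaten the design.

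**What to change.** In note 12 and the Part B schedule, add the same form:

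- before each dose on Days 2–7 (6 forms);
- on Day 8 before discharge (1);
- at the outpatient visit (1);
- at follow-up (1).

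Forms per subject rise from 2 × 7 = 14 to 14 + 9 = 23. For the once-daily 7-day course, recall coverage rises from 84 to 480 of 480 h. In section 16.1.6 or the separate statistical analysis plan, specify a summary of scores by treatment and time point, and compare form-derived AE counts only over periods when the form was given.

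At the least, reconcile 7.2.1 and 8.5.1 with note 12 by stating the questionnaire's actual window.

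The cost is nine more self-completed forms per subject, at times when subjects are already on the ward or attending, with no new visit or blood sample. The downside is that more low scores will be recorded as AEs in both arms under 14.2. A schedule change may need an amendment.
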